7.0 STUDY CALENDAR

7.1 Treatment Group

		Screening	Treatment Week						Pre-Op *5	Surgery *6	Post-Op									Year 2 and Year 3 +/- 1 month
		Day -14 to 0	Day 1	Day 2	Day 4*9	Day 15	Day 16	Day 19*9	Day 25 - 35	Day 28 - 38	Week 3 +/- 1 week	Week 6 +/- 1 week	3 months +/- 3 weeks	5 months +/- 2 weeks	6 months +/- 3 weeks	8 months +/- 1 month	9 months +/- 1 month	10 months +/- 1 month	12 months +/- 1 month	
1	Informed Consent	1																		
2	Inclusion/Exclusion Criteria	1																		
3	Complete Medical History	1																		
4	Concomitant Medications**	1	2		3	4		5	6		7	8	9	10	11	12		13	14	
5	Assessment of Symptoms	1	2	3 *8	4	5	6 *8	7	8		9	10	11	12	13	14		15	16	
6	ECOG Performance Status	1																		
7	Physical Examination	1	2		3	4		5	6		7	8	9	10	11	12		13	14	
8	Tumor Assessment *1	1	2		3	4		5	6											
9	CBC with differential	1				2			3											
10	CMP	1				2			3											
11	PT - PTT	1																		
12	Research Blood	1	2			3			4		5	6	7		8					9
13	Pregnancy Test	1*14	2			3			4*13											
14	CT Scan or MRI of the Head & Neck With and Without Contrast *2	1							2											
15	Tumor Measurements *3	1							2											
16	PET CT Scan *2	1							2 *7											
17	Pathology for Tissue Analysis *4	1							2											
18	HPV Testing (PCR) and p16 *4	1																		
19	Vaccine Administration		1			2														

		Screening	Treatment Week					Pre-Op *5	Surgery *6	Post-Op										
		Day -14 to 0	Day 1	Day 2	Day 4*9	Day 15	Day 16	Day 19*9	Day 25 – 35	Day 28 – 38	Week 3 +/- 1 week	Week 6 +/-1 week	3 months +/-3 weeks	5 months +/-2 weeks	6 months +/-3 weeks	8 months +/- 1 month	9 months +/- 1 month	10 months +/- 1 month	12 months +/- 1 month	Year 2 and Year 3 +/- 1 month
20	Vital Signs		1 *11																	
21	Lm Surveillance Monitoring*10											1		2		3			4	Every 4 months (5-10)
22	Dispense/ Prescribe Oral Prophylactic Antibiotics		1 *12																	

*1 Evaluate tumor or inflammation, size change or other indication of immune flare

*3 By RECIST 1.1

*5 Maximum 72 hrs before surgery

*7 Optional to patient (Desired but not required)

*9 Day 4 and 19 visits may be replaced by a phone call if patient is asymptomatic

*11 Monitor vital signs every 30 minutes (± 5 minutes) immediately prior to and for the first 6 hours following the completion of every ADXS11-001 infusion

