Each prepared dose of ADXS11-001 must be administered at room temperature (temperatures at or below 25°C [77°F]) within 6 hours from product vial removal from the freezer. This includes vial thaw, room temperature storage of the vial, dose preparation, storage of the infusion suspension in the IV bag and the duration of the infusion. Administer ADXS11-001 at room temperature intravenously over a 60-minute infusion time.

The time the vial is removed from the freezer is to be recorded (T0).

Doses will be administered to patients who have received the prophylactic medication specified in the protocol as a 60 minute intravenous (IV) infusion. The actual time of administration is to be recorded (T1). The actual time the infusion is completed is to be recorded (T2).

9.6 Drug Ordering and Distribution: Please see Appendix A.

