Do not substitute acetaminophen for the selected NSAID for prophylactic treatment since acetaminophen does not have similar anti-inflammatory properties that could ameliorate cytokine release symptoms.

- 10.2 After each vaccination, subjects will receive a 7-day course of oral antibiotic therapy starting approximately 72 hours after administration of ADXS11-001. Antibiotic therapy should consist of either 160 mg trimethoprim/800 mg sulfamethoxazole (DS) tablet administered three times a week for 7 days or 80 mg trimethoprim/400 sulfamethoxazole administered daily for 7 days. In subjects with a sulfa allergy, prophylactic antibiotic therapy should consist of ampicillin 500 mg four times daily for 7 consecutive days starting approximately 72 hours after administration of ADXS11-001.
- 10.3 Treatment is to be done on an outpatient basis. Patients will be observed in the outpatient area for 6 hours following the ADXS11-001 infusion. Vital signs will be taken pre-dose, and every 30 min for 6 hours after each dose.
- 10.4 Criteria for discharge from observation: At 6 hours after the dose, the patient must have a temperature less than 38.5 degrees C and other vital signs (heart rate, blood pressure, and respiration) must be within normal limits. The patient must not show signs or symptoms of moderate-severe nausea, vomiting, or headache. If the patient does not meet these discharge criteria, the patient should be admitted to the hospital for observation and treatment of side effects.

For those patients stable for discharge the study team will contact the patient by telephone at one and three days following administration of the vaccine to determine if any adverse events have occurred.

- 10.5 Safety follow-up will be conducted via a telephone call 30 days (± 5 days) after the last ADXS11-001 infusion or in week 1 visit post surgery to confirm the resolution of any ongoing AEs and SAEs. Subjects will also continue to be monitored for adverse and serious adverse events during the 3 year Lm surveillance monitoring period of the study.

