10.10 ADVERSE EVENTS AND SUPPORTIVE CARE: The most likely AEs associated with ADXS11-001 are comprised primarily of individual flu-like symptoms (e.g., fever, chills, body ache, and fatigue) or cytokine release symptoms (e.g., headache, nausea, vomiting, tachycardia, shortness of breath, hypotension and rash). The symptoms usually present within 2-4 hours after the completion of infusions and are often mild to moderate and transient in nature or responds quickly to symptomatic treatment. In rare instances they may last up to 24 hours. No cumulative toxicity has been observed.

Less likely AE's include increase heart rate, low blood pressure, muscle aches, headaches, allergic reaction, changes in blood chemistry, changes in blood counts, and short term changes in liver function.

Rare but serious AEs include high fever, difficulty breathing and hypotension.

Like all *Listeria*, ADXS11-001 has a tropism for the liver. Transient asymptomatic elevations of ALT and alkaline phosphatase were observed after dosing in the Phase 1 trial without prophylactic medication administration. For that reason, patients with significant liver disease are excluded, and particular attention is to be paid to hepatic abnormalities.

- 10.10.1 Supportive Care Guidelines: The major safety findings with ADXS11-001 occurring in $\geq 5\%$ of subjects, as of June 2016 (n=290) and being possibly, probably or definitely related include anemia (61.4%), chills (63.5%), fatigue (25.5%), fever (57.6%), nausea (36.9%), vomiting (30.3%), headaches (23.8%). Most are Grade 1-2 in severity. Subjects should receive appropriate supportive care measures as deemed necessary by the treating Investigator with consideration given to the criteria the items outlined below.

Nausea and vomiting- should be treated aggressively, and consideration should be given in subsequent cycles to the administration of prophylactic antiemetic therapy according to standard institutional practice. Subjects should be strongly encouraged to maintain liberal oral fluid intake.

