Cytokine Release Symptoms- are a constellation of inflammatory symptoms resulting from cytokine elevations associated with T cell engagement and proliferation. Symptoms related to cytokine release may include constitutional symptoms such as fever, chills, rigors, fatigue, headache, nausea, vomiting, rash, tachycardia, hypotension and shortness of breath which usually presents several hours after the infusion and lasts for up to 24 hours. These symptoms are caused by an increase in cytokines such as TNF α , IFN γ and IL-6, all of which have been shown to occur after ADXS11-001 administration, resulting from the body's immune response to the therapy. Although, symptoms are often Grade 1-2 and transient, resolving with symptomatic management within 30 minutes to 1 hour, in some instances (~6%) Grade 3-4 hypotension has been seen. Therefore, close monitoring of blood pressure is strongly recommended at baseline, and during the post-infusion period. Increased levels of IL-6 have been strongly associated with capillary leak which manifests as hypotension due to the cytokines involved. We have observed elevated IL-6 levels after infusion of ADXS11-001, with peak levels occurring 2-4 hours after infusion. Emerging evidence indicates that IL-6 antagonists, such as tocilizumab, have demonstrated good results in treating cytokine-induced hypotension [61, 62, 63, 64] and are therefore recommended for cases of severe hypotension refractory to supportive care (e.g., fluids and/or pressors).

The management of cytokine release symptoms and guidelines for subsequent treatment for subjects who have experienced these AEs are shown in the table below.

Table B Recommended Management Guidelines for Adverse Events Associated with Cytokine Release

Toxicity	NCI CTCAE Grade or Severity	Treatment	Modification for Subsequent infusions
Hypotension	1 Mild	
 Supportive care 	
 Increase pretreatment IV fluids (e.g., 500 ml -1L normal saline)
All other cytokine release symptoms (e.g. chills, rigors, fever, nausea, vomiting)	1	
 Supportive care 	
 No modification

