* Tocilizumab is a humanized, immunoglobulin G1k (IgG1k) anti-human IL-6R mAb approved for treatment of adult subjects with moderately to severely active rheumatoid arthritis (RA) who have had an inadequate response to Disease-Modifying Anti-Rheumatic Drugs (DMARDs), for the treatment of active polyarticular juvenile idiopathic arthritis (PJIA), and active systemic juvenile idiopathic arthritis (SJIA) in subjects 2 years of age and older. Tocilizumab works by preventing IL-6 binding to both cell-associated and soluble IL-6Rs. Although, it is not indicated for the treatment of cytokine release symptoms emerging clinical experience at several institutions has concluded that tocilizumab is an effective treatment for severe or life-threatening cytokine release symptoms. [61, 62, 63, 64]

Management of infusion reactions- While there is some overlap between the symptoms of cytokine release and infusion reactions, infusion reactions typically occur during the infusion, while symptoms associated with cytokine release typically occur after the infusion and are mediated by a different mechanism of action. Signs/symptoms of infusion reactions may include: allergic reaction/ hypersensitivity (including drug fever); arthralgia (joint pain); bronchospasm; cough; dizziness; dyspnea (shortness of breath); fatigue (asthenia, lethargy, malaise); headache; hypertension; hypotension; myalgia (muscle pain); nausea; pruritis/itching; rash/ desquamation; rigors/chills; sweating (diaphoresis); tachycardia; tumor pain (onset or exacerbation of tumor pain due to treatment); urticaria (hives, welts, wheals); vomiting.

Table C below shows the management guidelines for subjects who experience an infusion reaction associated with administration of ADXS11-001.

Table C: Management Guidelines for Infusion Reactions

NCI CTCAE Grade	Management

Grade 1 Mild reaction; infusion interruption not indicated; intervention not indicated
	
Increase monitoring of vital signs as medically indicated until the subject is deemed medically stable in the opinion of the Investigator.

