
Grade 2 Requires infusion interruption but responds promptly to symptomatic treatment (e.g., antihistamines, NSAIDS, narcotics, IV fluids); prophylactic medications indicated for ≤24 hrs.
	
 1. Stop Infusion and monitor symptoms. Additional appropriate medical therapy may include but is not limited to: 
 IV fluids Antihistamines NSAIDS Acetaminophen Narcotics 2. Increase monitoring of vital signs as medically indicated until the subject is deemed medically stable in the opinion of the Investigator. If symptoms resolve within one hour of stopping drug infusion, the infusion may be restarted at 50% of the original infusion rate. Otherwise dosing will be held until symptoms resolve and the subject should be premedicated for the next scheduled dose.

Grades 3 or 4
 
Grade 3: Prolonged (i.e., not rapidly responsive to symptomatic medication and/or brief interruption of infusion); recurrence of symptoms following initial improvement; hospitalization indicated for other clinical sequelae (e.g., renal impairment, pulmonary infiltrates)
 
Grade 4: Life-threatening; pressor or ventilatory support indicated
	
 3. Stop Infusion. Additional appropriate medical therapy may include but is not limited to: 
 IV fluids Antihistamines NSAIDS Acetaminophen Narcotics Oxygen Pressors Corticosteroids Epinephrine 4. Increase monitoring of vital signs as medically indicated until the subject is deemed medically stable in the opinion of the Investigator. 5. Hospitalization may be indicated. 6. Subjects who experience a Grade 4 reaction should be permanently discontinued from study. Subjects who experience a grade 3 reaction may be discontinued. Discussion with the Sponsor is recommended

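### No vital signs are scheduled while ADXS11-001 is running, although the protocol expects infusion reactions then and has staff stop the infusion for grades 2 to 4

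*Combined protocol and SAP*

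**What the plan says.** Three statements govern monitoring around each dose.

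- Section 10.3: "Vital signs will be taken pre-dose, and every 30 min for 6 hours after each dose".
- Study Calendar 7.1, footnote 11: readings every 30 minutes, with a 5-minute window either way, "immediately prior to and for the first 6 hours following the completion of every ADXS11-001 infusion".
- Section 10.10.1, on cytokine release: "close monitoring of blood pressure is strongly recommended at baseline, and during the post-infusion period".

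Section 9.5 sets the duration: "Administer ADXS11-001 at room temperature intravenously over a 60-minute infusion time". Table B extends a later infusion to 2 hours after grade 2 hypotension, or after other cytokine-release symptoms of grade 2 or 3.

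On timing, Section 10.10 says of flu-like and cytokine-release symptoms: "The symptoms usually present within 2-4 hours after the completion of infusions". Section 10.10.1 separates the two kinds of event: "infusion reactions typically occur during the infusion, while symptoms associated with cytokine release typically occur after the infusion". Section 3.2 adds that cytokine-release symptoms may appear during administration as well as in the hours after it.

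Table C begins its grade 2 instructions with "Stop Infusion and monitor symptoms", and grades 3 and 4 also start by stopping. Grade 1 calls for closer monitoring without interruption. If a grade 2 reaction settles within an hour, "the infusion may be restarted at 50% of the original infusion rate".

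**The concern.** The schedule suits cytokine release, which mostly appears hours later. It does not suit infusion reactions, which the protocol places inside the one interval that has no planned reading. Three of the listed signs (hypotension, hypertension and tachycardia) are found by measuring vital signs. Table C steps monitoring up only once a reaction has been recognised, so it cannot stand in for a routine reading that would reveal one.

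Two things are at stake. First, a fall in blood pressure with few or vague symptoms could go unmeasured while a live bacterial product is still being given, when stopping it is still possible. Second, a fall first measured after completion has no recorded onset, and onset is the main feature Section 10.10.1 uses to tell the two kinds of event apart. At grade 2 the choice matters. Table C leads to a stop and perhaps a half-rate restart. Table B leads to fluids and one pressor dose for hypotension, then a longer infusion, more pretreatment fluid and hydrocortisone premedication at the next dose.

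**Working it through.** The plan states no figure for the interval, so there is none to reproduce. The inputs are:

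- infusion time of 60 minutes (9.5), or 120 minutes if extended (Table B);
- reading interval of 30 ± 5 minutes (footnote 11);
- 6 hours of post-infusion readings (10.3, footnote 11);
- 2 infusions per patient (10.0);
- up to 22 vaccinated patients (16.0).

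I assume that the pre-dose reading falls at the start of the infusion and that all 22 patients receive both doses.

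**Current gap** = infusion time + time to the first post-infusion reading. The documents do not say whether a reading is taken at completion, so both ends are shown.

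| Infusion | Reading taken at completion | First reading 30 + 5 min after completion |
|---|---|---|
| 60 min | 60 min | 60 + 30 + 5 = 95 min |
| 120 min | 120 min | 120 + 30 + 5 = 155 min |

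No reading is scheduled during either infusion. The longest gap falls to patients whose first dose already caused grade 2 hypotension or other grade 2 or 3 cytokine-release symptoms.

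**Gap with readings every 30 ± 5 minutes and at completion.** For 60 minutes, readings at 0, 30 ± 5 and 60 give a longest gap of 35 minutes. For 120 minutes, readings at 0, 30 ± 5, 60 ± 5, 90 ± 5 and 120 give a longest gap of 65 − 25 = 40 minutes.

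**Reading counts.**

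- Now: 1 pre-dose + 6 h ÷ 30 min = 13 per infusion, so 13 × 2 × 22 = 572.
- Added if all infusions last 60 minutes: 2 × 2 × 22 = 88, and 88/572 = 15.4%.
- Added if every second dose lasts 2 hours: (2 + 4) × 22 = 132, and 132/572 = 23.1%.
- Where sites already read at completion, one fewer per infusion (2 × 22 = 44): 88 − 44 = 44, or 132 − 44 = 88.

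**Half-rate restart.** If a 60-minute infusion is stopped at minute t, the rest takes 2 × (60 − t) minutes. Stopped at minute 30, that is another 60 minutes, for which Table C fixes no reading interval once the patient is judged stable.

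**The case against.** The strongest reply is that the schedule follows the documented risk. Sections 2.3, 10.1 and 10.10 put typical onset 2 to 4 hours after infusion, and 12 readings cover that period. Section 10.10.1 discusses the roughly 6% rate of grade 3–4 hypotension under cytokine release. Table 1, limited to related events in at least 5% of subjects, lists no infusion-reaction term. This stands, and it rules out a tempting inference. A reader might take Table 1's 58/290 (20.0%) for hypotension, or 18/290 (6.2%) for grade 3–4, as the risk during infusion. The documents give no onset times and attribute the severe cases to a process that usually starts hours later, so neither figure measures that risk.

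A second reply is that staff would notice most reactions. Treatment is given in clinic, and most listed signs, such as rigors, rash or dyspnea, are seen or reported. Table C's wording on increased monitoring suggests that some checking is already under way. A mild silent fall would be grade 1, for which Table C does not stop the infusion. This narrows the harm to falls that need action yet show little, but no checking interval is specified. A reader might also infer that patients are left unattended or that every reaction requires a stop. The documents say neither.

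Third, misclassification matters less in severe cases. Both tables point to discussion with the sponsor for grade 3 hypotension and to permanent discontinuation for grade 4. The difference lies mainly at grade 2.

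Finally, footnote 11 is loosely worded and could be stretched to mean monitoring from before the infusion until 6 hours after it. Its reference to completion, read with Section 10.3, favours the narrower reading, and the ambiguity is itself a reason to clarify.

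**Conclusion.** The point holds as a minor gap in safety monitoring. A site that follows the schedule exactly takes no vital signs for 60 to 95 minutes around a standard infusion and 120 to 155 minutes around an extended one. The protocol itself expects infusion reactions in that interval. The stop instruction concerned is the one for grades 2 to 4 only.

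The benefit of closing the gap is real but modest, and the number of patients who would gain cannot be estimated from the documents. The T-cell go/no-go rule is unaffected. The conclusion rests on reading Section 10.3 and footnote 11 literally. The lower end of each range assumes a reading at completion, which footnote 11 neither requires nor excludes.

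**What to change.** In footnote 11 and Section 10.3, require vital signs at these times:

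- immediately before each infusion;
- every 30 (± 5) minutes while it runs, including after any interruption and restart;
- at completion (T2, a time that Section 9.5 already has sites record);
- every 30 (± 5) minutes for 6 hours after that.

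In Section 10.10.1, extend the blood pressure recommendation to cover the infusion period as well as baseline and afterwards. No new rule for choosing between Tables B and C is needed.

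The cost is at most 2 extra readings per 60-minute infusion and 4 per 2-hour infusion. Across 22 patients that is 88 readings if no dose is extended, with an upper bound of 132 if every second dose is. A half-rate restart adds about one reading per further 30 minutes. Closer measurement may find mild falls and prompt a few extra interruptions, although Table C does not ask for interruption at grade 1. Dose, eligibility and sample size do not change.

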- 10.6 Subjects will receive a 6 month course of oral trimethoprim/sulfamethoxazole or ampicillin for subjects with sulfa allergies to be initiated approximately 72 hours of resuming oral intake after transoral surgery, or at the time of study discontinuation. For those patients for whom resumption of oral intake is delayed beyond 72 hours, an alternative delivery route (e.g. gastrostomy tube) may be employed. Trimethoprim/sulfamethoxazole therapy should consist of either 160 mg trimethoprim/800 mg sulfamethoxazole (DS) tablet administered three times a week or 80 mg trimethoprim/400 mg sulfamethoxazole administered daily for 6 months. The dose of ampicillin consists of 500 mg four times daily for 6 months. Review the approved product labeling for Bactrim and ampicillin, and monitor antibiotic tolerance as dosing adjustments may be necessary.
- 10.7 Lm Surveillance Monitoring: In addition, all subjects will participate in a three-year Lm surveillance period. Surveillance monitoring for the detection of Lm will be initiated at the completion of study treatment according to the protocol or at the time of study discontinuation if earlier. This surveillance monitoring period will consist of a 6-month course of oral antibiotics, obtaining a blood sample to monitor CBC, CMP, including CRP and ESR, and blood cultures at regular intervals. This testing will be performed on all subjects who have received at least 1 dose of ADXS11-001. It will occur at 3 months (± 2 weeks), 6 months (± 3 weeks), 9 months (± 1 Month), 12 months (± 1 Month), and every 4 months (± 1 Month) for year 2 and year 3 postoperatively. If a persistent increase in CRP and/or ESR is observed with negative blood cultures for *Listeria* during this time, the subject should be evaluated and treated, as appropriate, for another possible cause. In the event that a definite cause has not been identified, subjects must continue to be monitored closely, including additional testing and a blood culture, for possible signs/symptoms of listeriosis. This testing may be performed at the investigational site or at another acceptable location following consultation with the study chair.
- 10.8 **Treatment modification:** The dose of ADXS11-001 will not be modified (i.e., reduced or increased). However, treatment may be delayed or discontinued based on toxicities, as shown below in Table A.

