10.10.3 Management and Surveillance of Listeria during Study Participation

In the event a subject experiences a persistent fever lasting 72 hours after receiving study treatment then the oral antibiotic regimen will be replaced by broad spectrum IV antibiotic treatment. If symptoms consistent with sepsis occur close to ADXS11-001 administration or at any time after ADXS11-001 administration, immediate medical attention must be sought. A microbial culture will be taken to identify the agent of sepsis and antibiotic sensitivity testing should be performed to confirm susceptibility. An infectious disease consult should be obtained for further management of these subjects.

All subjects will receive a 6-month course of an oral antibiotic regimen as a prophylactic measure approximately 72 hours following the completion of the last dose of ADXS11-001 treatment or at the time of study discontinuation. This additional safety measure is intended to eradicate *Lm* from the body.

Lm surveillance monitoring will also be initiated following the completion of the last dose of ADXS11-001 treatment or at the time of study discontinuation. This monitoring will include obtaining a blood sample for CBC, comprehensive metabolic panel (CMP), including CRP and ESR, and blood cultures for the detection of *Listeria*. Testing will be performed on all subjects who have received at least 1 dose of ADXS11-001 and occur 3 months(+/- 2 weeks), 6 months(+/- 3 weeks), 9 months(+/- 1 Month), 12 months(+/- 1 Month), and every 4 months(+/- 1 Month) for year 2 and year 3 postoperatively.

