12.0 SCHEDULE OF BLOOD AND SAMPLE COLLECTION

12.1 TREATMENT GROUP

1. The day of the first dose of vaccination will be considered “day 1”.
2. Standard-of-care pre-treatment tumor biopsy will be performed in a timely fashion for those patients without a prior biopsy, whose prior biopsy is inadequate for clinical planning, or for whom prior biopsy material adequate for immunophenotyping by immunohistochemistry (IHC) is not available.
3. Initial blood draw (Draw 1) will be obtained prior to the first vaccination usually during screening visit.
4. Draw #2 will be performed on the day of the first vaccination (e.g. day 1) before vaccine infusion.
5. Draw #3 will be performed on the day of the second vaccination (day 15) before vaccine infusion.
6. Surgery, and harvest of tumor and TIL, will be performed on day 35 +/- 7 days following entry into the study and baseline blood draw.
7. Draw #4 will be performed preoperatively, on the day of surgery prior to induction of anesthesia, or up to 72 hours prior to the surgery.
8. Draw #5 will be performed 3 weeks (+/- 1 week) after surgery.
9. Draw #6 will be performed 6 weeks (+/- 1 week) after surgery, before radiation.
10. Draw #7 will be performed 3 months (+/- 3 weeks) post-surgery.
11. Draw #8 will be performed 6 months (+/- 3 weeks) post-surgery.
12. Draw #9 will be performed 12 months (+/- 4 weeks) post-surgery.

12.1.1 LISTERIA SURVEILLANCE MONITORING BLOOD DRAW: Up to 45 ml of additional blood will be collected for safety follow up testing as *Listeria* surveillance monitoring. It will include CBC, CMP, including CRP and ESR and blood cultures for the detection of *Listeria*.

Patients in the control group will NOT undergo additional blood draw or monitoring. These blood draws will be performed at 3 months(+/- 2 weeks), 6 months(+/- 3 weeks), 9 months(+/- 1 Month), 12 months(+/- 1 Month), and every 4 months(+/- 1 Month) for year 2 and year 3 as mentioned in schedule above.

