- Live vaccines within 30 days prior to the first dose of trial treatment and while participating in the trial. Examples of live vaccines include, but are not limited to, the following: measles, mumps, rubella, chicken pox, yellow fever, rabies, BCG, and typhoid (oral) vaccine. Seasonal influenza vaccines for injection are generally killed virus vaccines and are allowed; however, intranasal influenza vaccines (e.g., Flu-Mist®) are live attenuated vaccines and are not allowed.
- Acetaminophen is not to be used for premedication but may be used for supportive care measures. NSAIDs, such as naproxen and ibuprofen have been evaluated and are confirmed not to interfere with efficacy.

Subjects who, in the assessment by the Investigator, require the use of any of the aforementioned treatments for clinical management should be removed from the trial. Subjects may receive other medications that the Investigator deems to be medically necessary.

15 Treatment Discontinuation:

Surveillance monitoring for the detection of *Lm* will be initiated at the completion of study treatment according to the protocol or at the time of study discontinuation if earlier. This surveillance monitoring phase will consist of a 6 month course of oral antibiotics, obtaining a blood sample to monitor CBC, CMP, including CRP and ESR, and blood cultures at regular intervals. This testing will be performed on all subjects who have received at least one dose of ADXS11-001. It will occur at 3 months(+/- 3 weeks), 6 months(+/- 3 weeks), 9 months(+/- 1 Month), 12 months(+/- 1 Month), and every 4 months(+/- 1 Month) for 2nd and 3rd year beginning after the last dose of study treatment. If a persistent increase in CRP and/or ESR is observed with negative blood cultures for *Listeria* during this time the subject should be evaluated and treated, as appropriate, for another possible cause. In the event that a definite cause has not been identified then subjects must continue to be monitored closely, including another additional testing and a blood culture, for possible signs/symptoms of listeriosis. This testing may be performed at the investigative site or at another acceptable location following consultation with the Sponsor.

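### Sections 10.6 and 10.10.3 give incompatible start points for the 6-month Listeria antibiotic course in patients who complete treatment, about 10 to 23 days apart

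*Combined protocol and SAP*

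**What the plan says.** **Start of the 6-month course.** Section 10.6 says it is "to be initiated approximately 72 hours of resuming oral intake after transoral surgery, or at the time of study discontinuation". Section 10.10.3 says "All subjects will receive a 6-month course of an oral antibiotic regimen as a prophylactic measure", beginning "approximately 72 hours following the completion of the last dose of ADXS11-001 treatment or at the time of study discontinuation".

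**Short courses.** Under section 10.2, after each vaccination "subjects will receive a 7-day course of oral antibiotic therapy starting approximately 72 hours after administration of ADXS11-001".

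**Other mentions of the 6-month course.** Sections 10.7 and 15 place it inside a surveillance period that begins when study treatment is completed, or at discontinuation if that is earlier. Footnote *12 of the study calendar mentions it only for a patient who discontinues. Section 13.0 describes it as following vaccination. None of these says whether 10.6 or 10.10.3 takes precedence.

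**Surveillance visits.** Sections 10.7 and 10.10.3 end the visit list with "for year 2 and year 3 postoperatively". Section 15 ends the same list with "for 2nd and 3rd year beginning after the last dose of study treatment". The 3-month visit has a window of ±2 weeks in 10.7, 10.10.3 and 12.1.1, and of ±3 weeks in section 15.

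**The concern.** The product is a live attenuated Listeria strain. Section 10.10.3 presents the 6-month course as a safety measure meant to clear the organism, and the protocol warns of delayed infection. The starting rule for that measure should therefore be unambiguous.

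As written, a site that follows one section departs from the other for every patient who completes both doses and goes to surgery. Two patients on the same schedule could have different prophylaxis in the weeks before the operation, depending on which section their site used. A deviation log could not say which of them was treated per protocol. If surveillance visits are also counted from different days, early cultures are not taken at the same time after exposure in all patients.

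**Working it through.** The plan states no figure for this point, so there is none to reproduce. The check sets the two rules on the protocol's own day scale.

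**Inputs**
- Last vaccination: Day 15. Section 12.1 says "Draw #3 will be performed on the day of the second vaccination (day 15) before vaccine infusion", and the calendar agrees.
- Surgery: Day 28 to 38 (study calendar, section 7.1). Section 12.1 gives day 35 ± 7, that is 28 to 42, counted from study entry.
- 72 hours = 3 days.
- Assumption: oral intake resumes on the day of surgery, which is the earliest case.
- The wording in 10.6 can mean within 72 hours of resuming oral intake or 72 hours after it, so the lag is taken as 0 to 3 days.

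**Start of the 6-month course**
- Section 10.10.3: 15 + 3 = about Day 18.
- Section 10.6, lag 0: Day 28 to 38.
- Section 10.6, lag 3: 28 + 3 = 31 to 38 + 3 = 41.
- Section 10.6 overall: about Day 28 to 41.

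**Difference between the rules** (10.6 start minus Day 18)
- Lag 0: 28 − 18 = 10 to 38 − 18 = 20 days.
- Lag 3: 31 − 18 = 13 to 41 − 18 = 23 days.
- Overall: about 10 to 23 days.
- With surgery on day 42 under section 12.1, taking study entry as Day 1: 42 + 3 − 18 = 27 days.
- Delayed oral intake adds to each figure.

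**Days without protocol-scheduled Listeria prophylaxis before the 6-month course**
- The 7-day course after dose 2 runs over about Days 18 to 24.
- Under 10.6 the gap is the start day minus 25: 28 − 25 = 3 days at the shortest, 41 − 25 = 16 days at the longest in the calendar window, and 45 − 25 = 20 days if surgery is on day 42.
- Under 10.10.3 the gap is 0, because the 6-month course begins on the same day as the 7-day course.

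**Surveillance origin (secondary)**

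Shift = surgery day minus last dose day: 28 − 15 = 13 to 38 − 15 = 23 days (42 − 15 = 27 under section 12.1). A visit on its nominal date from one origin falls outside the other origin's window when the shift exceeds the window.

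| Visit | Window | Outside if surgery is on |
|---|---|---|
| 3 months (10.7, 10.10.3, 12.1.1) | ±14 days | Day 30 or later (15 + 14 = 29 is still inside) |
| 3 months (section 15) | ±21 days | Day 37 or later (15 + 21 = 36 is still inside) |
| 6 months | ±21 days | Day 37 or later |
| 9 and 12 months, years 2 and 3 | ±1 month (about 30 days) | never, since 27 is below 30 |

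The surveillance row of the calendar is not used here, because its column alignment could not be relied on in the text available.

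**The case against.** Several points limit what can be claimed, and they stand.

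- A reader might infer that patients go through surgery with no antibiotic cover under 10.6. The documents do not support that. They do not describe perioperative surgical antibiotics, so only the absence of protocol-scheduled Listeria prophylaxis can be stated. Nor is an interval without scheduled antibiotics contradictory in itself. The undisputed schedule already has one: the course after dose 1 covers about Days 4 to 10 and the next begins about Day 18.
- A reader might infer that the overlap under 10.10.3 is a harm. Sections 10.2 and 10.6 list the same drugs, doses and frequencies, so the short course could simply be the first week of the long one.
- A reader might treat 13 to 23 days as a minimum difference. That holds only if 10.6 means 72 hours after oral intake resumes; read as within 72 hours, the lower end is 10 days.
- The surveillance mismatch is weaker than the antibiotic one. The two closing phrases may attach only to years 2 and 3, where the ±1-month window absorbs the shift. Section 15 is headed as treatment discontinuation, although its text also covers completion. The ±3-week window appears in that section alone and may be editorial.
- A reader might infer that adverse-event windows become non-comparable. The safety call is set separately in section 10.5, and section 17.4.1 keeps reporting of possibly vaccine-related or Listeria-related serious events open for the full three years.

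None of this reconciles 10.6 with 10.10.3. The latter is addressed to all subjects, so it cannot be read as a rule for a different subgroup.

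**Conclusion.** The contradiction between 10.6 and 10.10.3 stands for every patient who completes both doses and has surgery. The start of the 6-month course differs by about 10 to 23 days on the calendar's surgery window, and by up to about 27 days if surgery is on day 42 under section 12.1 with study entry taken as Day 1. Section 10.6 leaves about 3 to 16 days (up to about 20) without protocol-scheduled Listeria prophylaxis, up to and around surgery; section 10.10.3 leaves none. These figures assume that oral intake resumes on the day of surgery; later resumption widens them.

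What follows is that prophylaxis can differ between patients or sites. That it will differ cannot be said, since this depends on which section each site follows.

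The surveillance origin and the 3-month window are a secondary inconsistency. It matters mainly at 3 months, and at 6 months only if surgery is on Day 37 or later. The primary endpoint, sample size and two-stage decision rule are untouched.

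**What to change.** Reconcile sections 10.6 and 10.10.3, and align 10.7, 12.1.1, section 15 and calendar footnote *12 with the result. The protocol should then show, everywhere:

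- one start trigger for the 6-month course in patients who complete treatment, worded so that the 72-hour phrase has one meaning;
- one time origin for the surveillance visits, stated for all visits including months 3 to 12;
- one window per visit.

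Footnote *12 should also cover patients who complete treatment, since it now mentions the 6-month course only for those who discontinue. Notify sites of the reconciled text. The sponsor must decide which start point, origin and window apply; this review takes no position on which is right.

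The cost is protocol wording and a site letter. No change to the sample size or the analysis is needed.
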